## Overall strategy

### Overview

The overarching goal of this proposal is to perform brain  $^{18}\text{F}$ -FEOBV VACHT PET and MRI and detailed clinical and cognitive characterization in at least 12 (n=18 enrolled; Net target completion rate = 12) patients with LBD who are on stable doses of cholinesterase inhibitors, *i.e.*, at least 4 weeks. In exploratory Aim 2, we will use MRI-guided finite element models that are informed by FEOBV PET imaging to create participant-specific computer models of electrical current flow through the brain in order to optimize stimulation effects and more precisely target COTC hubs via tDCS in a target engagement study. Assessment of cognitive fluctuations will be measured by the Dementia Cognitive Fluctuation Scale (49). Details on the baseline (pre-) and post tDCS testing protocol are listed in the General Methods.

Design & subjects and consideration of **relevant biological variables**, such as gender and age: Cross-sectional neuroimaging-clinical correlation study with exploratory non-invasive neurostimulation target engagement study. Although LBD affects men more than women, we will place special emphasis on equal recruitment of women. We have no *a priori* rationale to expect the findings to differ as a result of sex but will directly evaluate sex differences. Effects of age will also be taken into account.

Timeline and milestones: Gross recruitment for the project will be 18 persons with probable DLB while anticipating 12-18% attrition (net recruitment target n=12). We will recruit and test 8-9 persons per year (approximately one every 2 months). Subject recruitment and testing will be completed within the first 10 months

of year 2 to allow statistical analysis and write-up of the study findings. *Milestones* of success are net completion of 6 persons for year 1 by 12 months and a total of 12 by 10 months in year 2.

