**Statistical analysis:** The primary objective of this proposal is to establish VAChT PET COTC neural network correlates of cognitive fluctuations. We will employ generalized linear mixed models (GLMM) to accommodate correlation via fixed and random predictor effects. GLMM has the advantage that it also allows for modeling of non-normal distributions and nonlinear models. The main predictors will be bilaterally averaged opercular, insular and anterior cingulum VAChT PET binding and the summed score of the 17-item Dementia Cognitive Fluctuation Scale (49). As LBD affect men more than women, gender will be included as a key biological variable in all analyses. Other co-variates will include measures of (motor) disease severity such as modified Hoehn and Yahr stage or MDS-UPDRS part III score, global cognition (MoCA), age, and levodopa equivalent dose and use of cholinergic drugs. Analysis of exploratory Aim 2 will use GLMM to evaluate the overall tDCS effects and regression analysis of the relationship between bilaterally averaged opercular, insular and anterior cingulum VAChT PET and tDCS changes in the Dementia Cognitive Fluctuations Scale. To avoid Type II error inflation correction for multiple testing will be performed. Statistical analysis will be performed by the Department of Radiology statistician [name].

**Expected results:** For aim 1, we predict that severity of cognitive fluctuations as measured by the Dementia Cognitive Fluctuation Scale (49) associate with greater cholinergic deficits in COTC network regions in patients with LBD. For our exploratory aim 2, we predict that tDCS targeting key hubs of the COTC neural network using VAChT PET-derived stimulation volumes will improve subjective and objective cognitive fluctuations in the LBD patients and as a function of the degree of cholinergic losses in the targeted regions.

**Sample size considerations:** Our main hypothesis will be tested using GLMM analysis. We have preliminary data obtained in persons with PD showing a correlation coefficient of  $R=0.59$  ( $P<0.001$ ) between COTC VAChT binding and attention/working memory functions yielding a power of  $>.95$  to find a significant correlation ( $P<0.05$ ). Exploratory aim 2 is a target engagement study to provide go/no go feasibility for future clinical trials.

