standard". The CMs provide quantitative values about the electrical field (E-field) in the targeted COTC neural network brain region(s) of each participant (note that values will be available for all brain regions but our primary analyses will focus on those involved in the COTC). Full details of CMs are available in the literature (72-75) and we will employ the most common approach, which involves finite element models (FEM) using the newly available ROAST pipeline (76). Once calculated, the E-fields can be visualized and values extracted for the desired regions of interest (COTC in our study). An example of this approach is shown above in Figure 5 and these models have been validated against intracranial recordings, e.g., (77). Given our prior review of the literature (78), we will develop montages that provide a minimum of 1 V/m to the key regions of each participant's COTC. This approach overcomes known limitations in the standard administration of tDCS and increases the probability of positive results. We aim for 10 sessions split as 3-5 per week (71), with 4-5 sessions during the first week. Doses of cholinesterase inhibitor drugs will be kept the same throughout the duration of the study.

Scientific rigor: All tests and neuroimaging procedures used in this proposal have been validated and protocols have been published. Both PET and MR neuroimaging assessments will follow established and published acquisition protocols. Neuroimaging analysis will include well-validated and widely used software packages and processing pipelines such as SPM12, FreeSurfer, FSL, and AFNI. All equipment for mobility testing is commercially available and vendor-provided (validated) outcome parameters will be used. The neuropsychological test battery includes tailored components for use in LBD patients (63). We will rigorously guard against Type I and Type II errors and correct all our statistical inferences with family-wise error and false discovery rate corrections where appropriate. This reproducible and rigorous methodological and analysis approach will ensure results and conclusions that can be replicated by other investigations.

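### Multiplicity correction is justified by the wrong error type, the primary test and its alpha are not fixed, and the stated power above 0.95 holds neither at 12 nor at 18 patients

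*Combined protocol and SAP*

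**What the plan says.** Three places bear on this point.

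- **Overall strategy, Statistical analysis.** The sentence on multiplicity reads "To avoid Type II error inflation correction for multiple testing will be performed". It names no method and no family of tests. The same paragraph says "The main predictors will be bilaterally averaged opercular, insular and anterior cingulum VAChT PET binding", together with the summed fluctuation scale score.
- **Overall strategy, Sample size considerations.** Preliminary Parkinson's disease data are cited as "showing a correlation coefficient of $R=0.59$ ( $P<0.001", for binding in the network as a single quantity against attention and working memory, "yielding a power of $>.95$ to find a significant correlation". The significance level given is 0.05, with no adjustment and no sample size. Recruitment is described in the Overview as "n=18 enrolled; Net target completion rate = 12".
- **General methods, Scientific rigor.** The team will guard against both Type I and Type II errors and "correct all our statistical inferences with family-wise error and false discovery rate corrections where appropriate".

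**The concern.** A multiplicity correction makes each test stricter. That limits false positives and, with the sample size fixed, makes false negatives more likely. The plan gives the opposite reason for correcting.

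The sentence matters because of what surrounds it. Aim 1 is the stated primary objective, it carries a hypothesis test, and it rests on very few patients. A statistician following the text could run one test on a composite, three separate hub tests at 0.05, or three hub tests at a stricter level. The power statement does not identify which. If the family is settled only after the data are seen, the error rate of the primary claim is uncontrolled. Meanwhile the reader is told that power exceeds 0.95 and that Type II error is being protected.

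**Working it through.** **Inputs.** From the documents: R = 0.59, alpha 0.05 and power above 0.95 (Sample size considerations); 18 enrolled and 12 completers (Overview). Assumed: a two-sided test, since sidedness is not stated; and, for the corrected case only, three hub tests with Bonferroni, so alpha = 0.05/3 = 0.0167.

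**Step 1. The plan's own figure.** By the Fisher z approximation, power ≈ Φ(√(N−3) × atanh(R) − z), with atanh(0.59) = 0.678 and z = 1.960 at two-sided 0.05.

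- N = 12: √9 × 0.678 = 2.033; 2.033 − 1.960 = 0.073; power 0.53.
- N = 18: √15 × 0.678 = 2.625; 2.625 − 1.960 = 0.665; power 0.75.

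Simulating the t test of the Pearson correlation in bivariate normal data gives 0.56 and 0.77. A one-sided test gives 0.65–0.69 and 0.84–0.86. The stated attrition of 12–18% would leave 18 × 0.88 = 15.8 to 18 × 0.82 = 14.8, so about 15 or 16 patients, with simulated power of 0.68–0.71.

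The figure above 0.95 is not reproduced in any of these cases. Power of 0.95 needs N = 32 two-sided or 27 one-sided, or a true R of about 0.84 at N = 12 or 0.74 at N = 18. With N = 86, the size of the Parkinson's disease imaging set in the preliminary data, power is essentially 1. The figure may therefore describe that set, but the documents do not link the two.

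**Step 2. If three hubs were Bonferroni-corrected (assumption).** At alpha 0.0167, z = 2.394.

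| N | Power at 0.05 (Fisher / simulated) | Power for one given hub with R = 0.59 at 0.0167 (Fisher / simulated) |
|---|---|---|
| 12 | 0.53 / 0.56 | 0.36 / 0.37 |
| 18 | 0.75 / 0.77 | 0.59 / 0.61 |

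The family size is undefined, so the range matters. At N = 12, two tests give 0.42–0.44, six give 0.27 and nine give 0.22–0.23.

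**Step 3. If 0.59 belongs to the three-hub mean.** The power sentence treats network binding as one quantity. With equal inter-hub correlation c, each hub then correlates at 0.59 × √((1+2c)/3) with the outcome: 0.48, 0.52 and 0.55 for c = 0.5, 0.65 and 0.8 (assumed values). Simulated power:

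| N | Composite at 0.05 | Any hub significant after Bonferroni |
|---|---|---|
| 12 | 0.56 | 0.43, 0.46, 0.47 |
| 18 | 0.77 | 0.65, 0.68, 0.69 |

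**Step 4. What a correction is for.** Three independent tests at 0.05 have a familywise Type I error of 1 − 0.95³ = 0.143. That is the quantity a correction reduces.

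**Step 5. Covariates.** The plan lists about six adjustment variables. Taking 0.59 as the partial correlation and replacing N−3 by N−9, uncorrected power is 0.22 at N = 12 and 0.53 at N = 18. The figures in Steps 1 to 3 are therefore on the favourable side.

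**The case against.** The strongest reply is that this is one mistyped word. The Scientific rigor paragraph names Type I error and lists familywise and false discovery rate methods, so the authors evidently know what correction is for. Replacing the word changes no planned analysis. That stands as far as the word goes, but the family, the method and the alpha of the primary test remain open after the edit.

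A reader might go further and infer that the primary test will be run at a stricter level than its power claim, and that this strips out much of its power. The documents do not support that.

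- The promise to correct is limited to where it is appropriate, so the primary test may be exempt.
- The plural in the predictors sentence also covers the fluctuation scale. The hub wording can mean one composite, or three terms in one model.
- Bonferroni is never named.
- The fall from 0.56 to 0.37 applies to one pre-chosen hub. If each hub itself has R = 0.59, the chance that at least one passes Bonferroni at N = 12 is 0.56–0.67, no lower than for the single uncorrected test. Under Benjamini-Hochberg, per-hub power is about 0.49.

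These objections limit the size of the correction's effect. They do not touch the mismatch in Step 1, which exists before any correction.

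**Conclusion.** The point holds in a limited form. The stated reason for correction is reversed, most likely by a slip. The plan leaves the primary test undefined in two respects: composite or separate hubs, and corrected or not. Its single power figure is stated only at an unadjusted 0.05, and the design does not deliver it: about 0.56 at 12 patients and 0.77 at 18, taking R = 0.59 and a two-sided test.

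Any further loss from correction depends on choices the plan has not made. It is nil if one composite is tested at 0.05. It is about 0.16–0.19 for a given hub under an assumed three-test Bonferroni. If the composite carries the 0.59, the chance of any significant hub falls short of the composite's power by about 0.09–0.13 at N = 12 (0.56 against 0.43–0.47) and 0.08–0.12 at N = 18 (0.77 against 0.65–0.69).

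All these figures also assume that a correlation seen in Parkinson's disease with attention and working memory carries over to the fluctuation scale in Lewy body dementia, which the documents do not show.

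**What to change.** 1. In the Statistical analysis paragraph, change 'Type II' to 'Type I'.
2. Name one primary test: the Dementia Cognitive Fluctuation Scale total against mean VAChT binding over operculum, insula and anterior cingulate, two-sided 0.05, without adjustment. This matches the single binding measure in the power sentence. A joint three-hub model or false discovery rate control across hubs would also be defensible, if fixed in advance with its own power.
3. Make the hub-level, alternative-network and secondary-outcome tests secondary, with Holm or false discovery rate adjustment and each family listed.
4. Replace the figure above 0.95 with power at the alpha and sample size actually used, shown for 12 to 18 patients, and state how covariates are handled.

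This is a change of wording in the analysis plan and needs no new data or visits. The costs are that hub-specific findings become secondary and the stated power of Aim 1 becomes visibly less favourable.

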## **Protection of Human Subjects**

### **i) Human Subjects**

Description of subject populations: LBD patients (n=18; M/F; 50-90 years) who have cognitive fluctuations and who are on stable doses of cholinesterase inhibitors (i.e., at least 4 weeks) will be recruited to participate in this study. DLB patients will meet the Fourth consensus report of the DLB Consortium inclusion criteria for probable DLB (2). Subjects will be identified according to the following recognized DLB features: spontaneous parkinsonian motor signs, fluctuating attention and concentration, recurrent well-formed visual hallucinations, presence of REM behavioral sleep disturbance, anosmia/hyposmia, or autonomic dysfunction (2). PDD patients will meet the criteria by Emre *et al.* (88).

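### The stated power above 0.95 for the main hypothesis is not attainable: a correlation of 0.59 gives about 0.56 with 12 completers and about 0.77 with all 18 enrolled

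*Combined protocol and SAP*

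**What the plan says.** The power statement is in the Sample size considerations paragraph. It says the main hypothesis will be tested by a generalized linear mixed model (GLMM), and then: "We have preliminary data obtained in persons with PD showing a correlation coefficient of" 0.59 (P<0.001) "between COTC VAChT binding and attention/working memory functions yielding a power of" more than 0.95 at P<0.05. The sentence gives no sample size and no sidedness.

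The sample size is in Specific Aim 1 and in the Overview: "n=18 enrolled; Net target completion rate = 12". Timeline and milestones repeats a net target of 12, although its stated attrition of 12-18% would leave 15 to 16 of 18.

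The Statistical analysis paragraph names the outcome as the summed 17-item Dementia Cognitive Fluctuation Scale. The predictors are binding in the opercular, insular and anterior cingulate hubs. The covariates are gender, motor severity, MoCA, age, levodopa equivalent dose and cholinergic drug use. A correction for multiple testing is promised. The Human Subjects section restricts entry to patients "who have cognitive fluctuations and who are on stable doses of cholinesterase inhibitors".

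**The concern.** A correlation of 0.59 is large, but 12 to 18 patients is too few to detect it with 95% power. The sentence sits under Sample size considerations, directly after the main hypothesis, so a reader will take it as this trial's power.

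Two things are at stake. First, a non-significant Aim 1 result would be read as strong evidence against the cholinergic hypothesis, when a true correlation of 0.59 would be missed about 44% of the time at 12 completers (1 - 0.56). Second, at n=12 only an observed correlation of at least 0.576 in absolute value is significant. Significant estimates will therefore tend to be too large, and the plan intends positive findings to support a larger application.

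The effect size is also borrowed. It comes from a different disease group and a different outcome. The trial recruits patients because they have fluctuations, which may narrow the range of the fluctuation score and weaken its correlation with binding.

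**Working it through.** **Inputs from the plan.** r = 0.59, alpha 0.05 and claimed power above 0.95 (Sample size considerations); 18 enrolled and 12 completers (Specific Aim 1, Overview); attrition 12-18% (Timeline and milestones), leaving 18 × 0.88 = 15.8 to 18 × 0.82 = 14.8, that is 15 to 16.

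**Assumption.** Two-sided test, since sidedness is not stated; one-sided is shown as well.

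**Attempt to reproduce the plan's figure.** Fisher's z transform gives power ≈ Φ(atanh(r)·√(n−3) − 1.96), with atanh(0.59) = 0.678.

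- n = 12: 0.678 × 3 − 1.96 = 0.07, power 0.53.
- n = 18: 0.678 × 3.873 − 1.96 = 0.66, power 0.75.

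This approximation is slightly pessimistic in small samples, so three other methods were run: Fisher's z with a bias term and a t-based critical value, simulation of the Pearson test under bivariate normality (400,000 replicates), and the noncentral t with the predictor treated as fixed.

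| n | Fisher z, two-sided | Bias-corrected, two-sided | Simulation, two-sided | Noncentral t, two-sided | Simulation, one-sided |
|---|---|---|---|---|---|
| 12 | 0.53 | 0.56 | 0.56 | 0.63 | 0.69 |
| 15 | 0.65 | 0.67 | 0.68 | 0.74 | 0.79 |
| 16 | 0.69 | 0.71 | 0.71 | 0.78 | 0.82 |
| 18 | 0.75 | 0.77 | 0.77 | 0.83 | 0.86 |

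The most generous combination, a one-sided noncentral t with all 18 patients, gives 0.907. The claimed figure is not reproduced by any of these.

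**Sample size for 0.95.** n = ((1.96 + 1.645)/0.678)² + 3 ≈ 31.3, so 32 by Fisher's z; 31 with the bias correction; 27 by the fixed-predictor noncentral t.

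**True correlation needed for 0.95.** tanh(3.605/√9) = 0.83 at n=12 and tanh(3.605/√15) = 0.73 at n=18 (0.82 and 0.72 with the bias correction).

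**Correlation detectable with 80% power.** tanh(2.80/√9) = 0.73 at n=12 and tanh(2.80/√15) = 0.62 at n=18 by Fisher's z; about 0.71 and 0.61 by simulation.

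**Precision at n=12.** With 10 degrees of freedom the critical t is 2.228, so the critical correlation is 2.228/√(2.228² + 10) = 0.576. For an observed 0.59 the 95% CI is tanh(0.678 ± 1.96/3), that is 0.02 to 0.87.

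**Sensitivity, each under a stated assumption.**

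- Six covariates, with 0.59 taken as the partial correlation (√(n−3−6) replaces √(n−3)): 0.22 at n=12 and 0.53 at n=18 by Fisher's z.
- Bonferroni over the three hubs (alpha 0.0167; the plan does not specify this correction): about 0.36-0.37 at n=12 and 0.59-0.61 at n=18.
- True correlation of 0.4 to 0.5 in this population: 0.26 to 0.40 at n=12.

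**The case against.** **The power sentence gives no sample size, so it may describe the preliminary Parkinson's data.** A correlation of 0.59 with P<0.001 needs at least 28 patients, and a power above 0.95 fits a sample of about 31 or more. This may explain the number, but it is an inference. If it is right, the figure describes another dataset and still needs replacing.

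**If 0.59 were R-squared, power at n=18 would be 0.98.** The text calls it a correlation coefficient, and at n=12 that reading gives only 0.86-0.88.

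**Twelve is the least favourable sample size.** The Overview speaks of at least 12, the stated attrition leaves 15 to 16, and patients lost during stimulation could still contribute baseline data to a cross-sectional aim. That is fair, and the near-even odds of missing the effect apply only at n=12. But Specific Aim 1 itself carries the target of 12, and none of 15, 16 or 18 comes near 0.95.

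**The recomputed figures are not the power of the planned GLMM.** This stands. The values 0.56 and 0.77 are for one unadjusted Pearson test, the comparison the plan's own sentence describes. They are a benchmark and must be labelled so. The covariate and multiplicity calculations above lower them; the three-hub correction is illustrative only.

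**This is a small preliminary grant.** A small sample is acceptable. But Aim 1 is the primary objective, only Aim 2 is labelled exploratory, and a small study should not claim power it lacks.

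**Conclusion.** The concern holds. At the planned 12 completers, power is overstated by about 39 percentage points (0.95 − 0.56), and with all 18 enrolled by about 18 (0.95 − 0.77). These figures assume a true correlation of exactly 0.59, bivariate normality and one unadjusted two-sided test at 0.05. Choosing among standard methods or a one-sided test moves the values but does not reach 0.95 at 12 to 18 patients. If the correlation is weaker in Lewy body dementia patients selected for fluctuations, or if covariate adjustment and multiplicity are taken into account, the shortfall is larger. The paragraph must be corrected, because no other power figure supports the main hypothesis.

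**What to change.** In Sample size considerations:

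- Replace the claim of power above 0.95 with about 0.56 at 12 completers and about 0.77 at 18, stating that these apply to a true correlation of 0.59 and one unadjusted two-sided test at 0.05.
- Say that the planned covariates and multiplicity correction are not included and would reduce power. If the sponsor prefers to give power for the GLMM, it should state the model, sample size, sidedness and correction used.
- Give the correlation detectable with 80% power: about 0.71-0.73 at n=12 and 0.61-0.62 at n=18.
- State that 0.59 comes from Parkinson's disease patients and an attention/working-memory measure.
- State that a non-significant Aim 1 result does not refute the hypothesis.

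It would also help, though the correction does not depend on it, to present Aim 1 as estimation of the correlation with its 95% CI, using 0.02 to 0.87 (for 0.59 at n=12) to show the expected precision.

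The cost is a rewritten paragraph and a less favourable stated figure. No patients or procedures change.

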## General methods

**Clinical characterization:** All subjects will undergo a general clinical assessment. Severity of motor parkinsonism will be assessed using the Movement Disorder Society-revised Unified Parkinson's Disease Rating Scale (MDS-

UPDRS) (51). Neuropsychological testing measures are presented in Table 1. Neurobehavioral and sleep assessment will consist of Epworth Sleepiness Scale for daytime somnolence (52); The Mayo Sleep Questionnaire for sleep quality and disturbances (53); The Spielberger State Trait Anxiety scale for trait anxiety levels (54). The Brief Psychiatric Rating Scale will be used for the assessment of hallucinations (55). We will use the Geriatric Depression Scale for the assessment of depression (56). The Apathy Evaluation Scale (AES) clinician version will be used to assess apathy severity (57). Patient on dopaminergic medications will be testing in the medication 'on' state. The test battery will be repeated after the target engagement tDCS study.

